Several modalities of treatment for amblyopia are available, yet occlusion treatment is the gold standard involving covering the good eye with a patch for a prescribed period of time ranging from 10 minutes daily to all waking hours **(Von Noorden and Campos, 2002; Stewart et al., 2005)**. However, its effectiveness decreases in older children and adults **(Pediatric Eye Disease Investigator Group, 2005)**

Disadvantages include prolonged treatment leading to poor compliance, patching related distress, relationship strain and stigma. In extreme cases, non-compliance with patching results in a costly hospital admission to supervise the patching treatment. In addition, wearing a patch eliminates any advantage of binocularity **(Dixon-Woods et al., 2006)**. Not to mention that not all patients respond to patching and of those who do, many have residual amblyopia after treatment is stopped regardless of compliance **(Hess et al., 2014)**. More importantly, binocular vision is not automatically restored once the vision in the amblyopic eye has been improved. In fact, once

the patch is removed after therapy, the amblyopic eye could be suppressed by the better seeing eye and can lose some of the gains achieved as a result of therapy. **(Birch, 2013)**

Another modality of treatment is atropine eye drops and optical penalization which are usually secondary treatments to failed patching but carrying the same disadvantages as the ordinary patching **(Foss et al., 2013)**

Advances in amblyopia treatment include dichoptic training, perceptual learning, and video gaming **(Tsirlin et al., 2015)**. These depend on the fact that the adult brain has been shown to be much more plastic than it was once believed to be and hence have the advantage of expanding the age of response in adults. **(Pizzorusso et al., 2002; He et al., 2006)**

Perceptual learning approaches have the advantage of being a dichoptic (binocular treatment) approach which is independent of age and type of amblyopia. **(Polat et al., 2004; Levi and Li, 2009)** Furthermore, it has been shown recently that therapy promotes binocular vision by strengthening stereopsis and reducing suppression **(Hess et al., 2010; Hess et al., 2011)**

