A step further to conventional treatment is the use of a home-based approach allowing remote internet monitoring of treatment between office visits and hence better compliance. **(Hess et al., 2014)** In addition a video game version of the treatment is developed to make it more enjoyable for improving compliance. **(Foss et al., 2013)**. Moreover, dichoptic presentation can be achieved on the iPod device using a lenticular overlay screen. The advantage of using a lenticular overlay screen is that the luminance contrast is preserved **(Hess et al.; 2014)**

Aim of the work:

The aim of this work is to compare the gold standard occlusion therapy alone with dichoptic therapy

Patients and Methods:

Design:

The study will be a prospective experimental controlled study.

Patients of the study:

From the vicinity of the ophthalmology outpatient clinic of Ain Shams University Hospital, 100 patients of both sexes with amblyopia will be enrolled to this study. Informed consents will be obtained from adult patients and children's parents.

Patients will be assigned randomly into two groups:

Group A: 50 patients will receive the gold standard occlusion therapy

Group B: 50 patients will receive dichoptic treatment in the form of playing a video game (Lazy Eye Tetris games such as Lazy Eye Blocks ®) while wearing a red/green goggle.

Each group will be subdivided according to age:

1. From 4 to 7 years.
2. From above 7 to 12 years.
3. From above 12 to 30 years.

Hours of occlusion will be classified according to the degree of amblyopia:

- Mild to moderate amblyopia (Best corrected visual acuity (BCVA) < 0.2): 2-4 hours occlusion
- Severe (BCVA > 0.2): 4-6 hours occlusion

Hours of dichoptic treatment in group B will be classified according to the degree of amblyopia:

- Mild to moderate amblyopia (BCVA < 0.2): 2-4 hours of treatment
- Severe (BCVA > 0.2): 4-6 hours of treatment

Inclusion Criteria:

- Any degree of amblyopia
- Orthotropia in primary position.

Exclusion Criteria:

- Any ocular disease affecting vision
- Angle of deviation in primary position (Heterotropia)
- Adult patients and children's parents unwilling to enter or complete the study
- Ignorance of patients to use the video game

Methods

All patients will undergo the following:

- 1) Full medical and ophthalmic history
- 2) Examination:
 - A) External Appearance:
Anomalous Head Posture, globes (e.g., proptosis), lids (e.g. ptosis).
 - B) Refraction:
With and without cycloplegia.

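### Earlier and ongoing patching play no part in entry, allocation or analysis, so the arm difference is valid for the patients enrolled but cannot be interpreted by line of treatment

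*Protocol*

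**What the plan says.** In the protocol's Patients and Methods, the two inclusion criteria are "Any degree of amblyopia" and "Orthotropia in primary position". The four exclusions are "Any ocular disease affecting vision", heterotropia, unwillingness to take part, and inability to use the video game. None of the six concerns earlier or current treatment.

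On allocation, the protocol says "Patients will be assigned randomly into two groups" (50 to occlusion, 50 to dichoptic treatment) and names no stratification factor. It adds that "Each group will be subdivided according to age", in three bands covering 4 to 30 years. It does not say whether the bands govern allocation or only reporting.

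Under Methods, every patient has a "Full medical and ophthalmic history". Patching is not named as an item, and the history has no stated use in eligibility, allocation or analysis.

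The SAP specifies a one-way ANOVA for the effect of measurement time on acuity, with pairwise comparisons against baseline. It has no term or subgroup for treatment history and no between-arm test of acuity.

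The protocol's background, before the Aim, says that "not all patients respond to patching and of those who do, many have residual amblyopia after treatment is stopped regardless of compliance". It also says that after the patch is removed "the amblyopic eye could be suppressed by the better seeing eye and can lose some of the gains achieved as a result of therapy".

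**The concern.** The stated aim is to compare occlusion with dichoptic therapy. Recruitment is from a hospital eye clinic, for a condition whose standard treatment is patching, and the age limit is 30. Previously or currently patched patients are therefore plausible entrants, and nothing in the criteria keeps them out.

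The same history means something different in each arm. For a patient patched earlier, Group A repeats a known treatment and Group B starts a new one. For a patient patching at entry, Group A continues. Group B is described only as receiving dichoptic treatment, which I read as a switch. Balanced numbers between arms do not remove this difference.

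What is at stake is interpretation. If the mix is neither recorded nor reported, a reader cannot tell whether a difference, or its absence, applies to new patients, to those with residual amblyopia after patching, or to those taken off a patch.

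**Working it through.** **Step 1: is there a rule anywhere?** The places where one could stand are the two inclusion criteria, four exclusion criteria, allocation sentence, age subdivision, baseline examination list, follow-up paragraph and SAP. None mentions earlier patching, current patching, a stop date or a run-in. The general history is the only place where the information could be captured.

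**Step 2: a figure to reproduce.** There is none. The total of 100 patients comes with no alpha, power, SD or target difference, and the documents give no share of previously or currently patched patients. All effect sizes, shares and SDs below are assumptions.

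**Step 3: repeat treatment.** Suppose both treatments gain 0.20 logMAR in never-patched patients, while earlier non-responders gain 0.05 on occlusion and 0.20 on dichoptic treatment. With a share p of earlier non-responders, the pooled difference is p × (0.20 − 0.05):

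- p = 0.2: 0.03
- p = 0.5: 0.075
- p = 0.8: 0.12

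All favour dichoptic treatment. The SAP's 0.125 logMAR is a threshold for improvement, used here only as a yardstick. If earlier non-responders gained 0.05 on both treatments, the shift would be p × (0.05 − 0.05) = 0.

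**Step 4: continuation versus switch.** If 30% are patching at entry and lose 0.10 logMAR in Group B, that arm falls by 0.3 × 0.10 = 0.03. Combined with p = 0.2 from step 3, the net is 0.03 − 0.03 = 0.

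**Step 5: a wider assumed range.**

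- Group A: 20–60% gain 0.05–0.10 less, so the mean falls by 0.2 × 0.05 = 0.01 to 0.6 × 0.10 = 0.06.
- Group B: 10–40% lose 0.05–0.10, so the mean falls by 0.1 × 0.05 = 0.005 to 0.4 × 0.10 = 0.04.
- Net towards dichoptic treatment: from 0.01 − 0.04 = −0.03 to 0.06 − 0.005 = +0.055.

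The sign is not determined.

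**Step 6: chance imbalance without stratification.** These are exact binomial sums with 50 per arm. If 20% were previously patched, the arms differ by 10 percentage points or more with probability 0.26. At 40% or 60% the probability is 0.36. A gap of 20 points or more has probability 0.02 and 0.05 respectively.

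**Step 7: what a subgroup result can deliver.** Assume SD 0.20, an even never/ever split and no losses.

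- Whole trial: 95% half-width 1.96 × 0.20 × √(2/50) = 0.078.
- One subgroup, 25 per arm: 1.96 × 0.20 × √(2/25) = 0.111.
- Interaction: SE = √2 × 0.20 × √(2/25) = 0.08. For an interaction of 0.15, power is Φ(0.15/0.08 − 1.96) = Φ(−0.085), about 47%. At SD 0.25 the SE is 0.10 and power is Φ(−0.46), about 32%.

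**The case against.** The strongest reply is that this is effect modification, not bias. The protocol claims neither first-line nor treatment-naive use, and a randomised difference validly estimates the average effect in the patients enrolled. That stands. Four stronger readings are tempting, but the documents do not support them.

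- **The comparison is biased towards one arm.** The two mechanisms lower different arms and can cancel (step 4). Step 3 also assumes its own conclusion, that earlier non-responders do well on dichoptic treatment and poorly on occlusion.
- **The false-positive rate is inflated.** With a net shift of 0.04 logMAR and an assumed SD of 0.20 or 0.25, a two-sided 5% test would be significant with probability 0.17 or 0.13 when never-patched patients show no difference. That is power to detect a real average difference in the enrolled mix. It would be an error only if the result were presented as applying to never-patched patients.
- **Group A re-treats failures, mostly in the older bands.** The background separates non-responders from responders with residual amblyopia, and the latter did not fail. It also lists poor compliance as a drawback, so earlier non-response need not predict failure of repeat treatment. No text gives treatment history by age.
- **Group B carries withdrawal loss.** The background describes loss after patching ends, through suppression by the better eye. It also says the newer therapy reduces suppression. It does not describe loss on a direct switch to dichoptic treatment.

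It can also be said that the SAP contains no between-arm comparison to which a covariate could be added. That is true and belongs in the fix. None of this supplies the missing information on who was patched before entry.

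**Conclusion.** The point holds as a gap in design and reporting. Entry, allocation and analysis take no account of earlier or ongoing occlusion, although the protocol's background gives reasons why it could matter. The pooled randomised difference is valid for the enrolled mix. Without patching history it cannot be interpreted by line of treatment, and continuation versus switch cannot be separated from the comparison of interest.

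Size and net direction are unknown. The range in step 5 rests entirely on assumed shares and effects and shows only that either sign is possible. That some entrants will have been patched is an inference from the recruitment setting, not a statement in the documents.

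A reader might infer that any claim against occlusion should rest on never-patched patients alone. The documents do not require this, and with about half the sample the interval would be nearly as wide as the SAP's threshold on each side (0.111 against 0.125).

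**What to change.** - Name occlusion history as an item within the ophthalmic history already taken: never, earlier, or current at entry, with stop date. Tabulate it by arm.
- Stratify randomisation by never versus ever patched.
- Specify in the SAP a between-arm comparison of acuity change, with this factor as a covariate. The covariate deals with chance imbalance. It does not remove a difference in effect between the groups, so the next two items are also needed.
- Keep the pooled estimate as the main result and report the arm difference by patching history as a prespecified descriptive subgroup analysis.
- Repeat the comparison without patients who were patching at entry.

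Whether current patchers are eligible, and whether any off-treatment interval applies, is for the investigators to state.

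The cost is one history item, one two-level factor and a few lines of SAP text. If the age bands are also used as strata, 3 × 2 = 6 strata average about 17 patients each (100/6), or about 8 per arm. Subgroup estimates will be imprecise and an interaction test will have low power (step 7), hence the descriptive label. The history can be collected late, but stratification must be settled before randomisation and the analysis specified before outcome data are examined.

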 - C) Visual acuity:
With and without correction using Snellen acuity chart and preferential looking test for non-verbal patients.
 - D) Motility:
Ductions and versions (9 positions of gaze)
 - E) Angle of deviation if any
 - F) Fixation :
Fixation behavior (fixation preference) will be tested via base down 10 PD fixation preference test.
 - G) Quantitative Binocular vision assessment
 - H) Anterior segment examination.
 - I) Posterior segment examination using indirect ophthalmoscopy with a 20-D (diopter) lens through a dilated pupil.

All patients in Group A will receive the gold standard occlusion therapy. All patients in Group B will receive dichoptic treatment

Treatment assessment:

All patients will be followed up in the following schedule: after 1 month, after 2 months and after 6 months with regards to visual acuity. Patients who fail to complete the full time of the follow up period will be excluded from the study.

References:

- 2) Aldebasi YH. Prevalence of amblyopia in primary school children in Qassim province, Kingdom of Saudi Arabia. *Middle East Afr J Ophthalmol.* 2015;**22**(1):86-91
- 3) American Academy of Ophthalmology Basic and Clinical Science Course Subcommittee. Basic and Clinical Science Course. Pediatric Ophthalmology and Strabismus: Section 6. San Francisco, CA: American Academy of Ophthalmology. 2012.pp.61.
- 7) Birch EE. Amblyopia and binocular vision. *Progress in retinal and eye research* 2013;**33**:67-84

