A Comparative Study between Dissociative Treatment and Binocular Interactive Treatment in Amblyopia

Thesis

Submitted to Faculty of Medicine – Ain Shams University
In Partial Fulfillment of the Requirements of Doctorate Degree in Ophthalmology
By

[name]

M.B,B.C.h (2009) , M.Sc (2014) ,

Faculty of medicine - Ain Shams University

Under supervision of

[name]. [name]

Professor of Ophthalmology
Faculty of medicine – Ain Shams University

[name]. [name]

Professor of Ophthalmology
Faculty of medicine – Ain Shams University

[name] [name]

Lecturer of Ophthalmology
Faculty of medicine – Ain Shams University

[name] [name]

Lecturer of Ophthalmology
Faculty of medicine – Ain Shams University

Faculty of medicine
Ain Shams University
Cairo – Egypt
2017

STATISTICAL ANALYSIS PLAN

Using the SPSS (or the Minitab or Mega Stat) statistical software, the data will be examined using standard summary statistics which will include, where appropriate, 95% confidence intervals.

A one-way analysis of variance (ANOVA) will be performed on the visual acuity data to determine whether there appeared to be an effect of measurement time on visual acuity, and pairwise comparisons of mean will then be performed, examining the changes from baseline to 1 month, 3 months and 6 months after treatment start.

An improvement of ≥ 0.125 LogMAR units will be considered clinically significant. In addition, the proportion of change will be calculated at 1 month, 3 months and 6 months follow up as follows (using the formula described by Stewart et al)

$$\text{Proportion of change} = \frac{VA_{as} - VA_{ae}}{VA_{as} - VA_{fe}}$$

Where VA_{as} is the vision of amblyopic eye at baseline, VA_{ae} is the vision of amblyopic eye at the end of the treatment (i.e. 6months) and VA_{fe} is the vision of the non-amblyopic eye at the end of the treatment.

Also percentage of compliance with treatment in each group will be measured as a secondary outcome measure.

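### Snellen acuity is judged against a 0.125 LogMAR threshold; if the chart is read by whole lines, its coarse, unequal steps add avoidable noise that letter scoring on an equal-step chart would reduce

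*Protocol*

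**What the plan says.** Protocol, Methods, Examination, item C (Visual acuity) names the instrument: "With and without correction using Snellen acuity chart and preferential looking test for non-verbal patients". Under Treatment assessment, patients are followed "after 1 month, after 2 months and after 6 months with regards to visual acuity", so acuity is the only outcome that section names.

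The SAP uses the same readings in three ways:

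- "A one-way analysis of variance (ANOVA) will be performed on the visual acuity data", followed by pairwise comparisons of mean change from baseline.
- "An improvement of ≥ 0.125 LogMAR units will be considered clinically significant".
- A formula, applied at each follow-up, that divides the amblyopic eye's gain by its starting gap from the other eye.

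LogMAR is the only acuity unit the SAP names. Neither document states the chart's line set, whether it is scored by line or by letter, how a Snellen reading becomes a LogMAR value, how that value is rounded, or how repeatable a reading is. Nor do they say how preferential-looking results enter the LogMAR data, or whether 0.125 is a rule for each patient or a yardstick for a mean change.

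**The concern.** A Snellen chart has unequal steps on the LogMAR scale, and many of them are as large as the SAP's threshold. If one line is the smallest change recorded, then on a common metric layout a patient who reads one more line by chance has moved by about 0.125 or more.

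Two consequences follow. If 0.125 is applied patient by patient, some unchanged patients in both arms are counted as improved, which shrinks any difference in improvement rates. Whether or not it is applied that way, coarse steps add variance to every change from baseline, and so to the mean comparisons and the proportion of change. With 50 patients per group, each split into three age bands, avoidable variance is worth removing if that is cheap.

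**Working it through.** **Inputs from the documents:** Snellen chart (protocol, item C); threshold 0.125 LogMAR (SAP); 50 patients per group (protocol). The documents derive neither the threshold nor the sample size, so there is no plan calculation to reproduce.

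**Assumed:** the three chart layouts below; whole-line reading; true acuity uniform from 0.15 to 0.95 LogMAR; independent normal reading error at each of two visits, with the same SD for both scoring methods.

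**Step 1: line sizes.** Step = log10(MAR of a line / MAR of the next better line).

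- Metric, 6/60 to 6/6: log10(60/36) = 0.222; 36/24 gives 0.176; 24/18 gives 0.12494; 18/12 gives 0.176; 12/9 gives 0.12494; 9/6 gives 0.176. All six reach 0.125 if rounded to three decimals, but only four of six unrounded. A further 6/5 line would add a step of 0.079.
- 20-foot, 20/200 to 20/20: 0.301, 0.155, 0.146, 0.097, 0.125, 0.079, 0.097. Four of seven reach the threshold rounded, three unrounded.
- Decimal, 0.1 to 1.0 in tenths: from 0.301 (0.1 to 0.2) down to 0.046 (0.9 to 1.0). Three of nine reach it rounded, two unrounded.

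So the threshold is about one metric line. Whether 6/24 to 6/18 or 6/12 to 6/9 counts depends on a rounding rule that is not given.

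**Step 2: apparent improvement with no true change.** 400,000 simulated patients, error SD 0.06. Ranges cover recording the best line read or the nearest line.

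| Scoring | Gain of at least 0.125, steps rounded | Unrounded | SD of measured change |
|---|---|---|---|
| Metric lines | 19-20% | 12.6% | 0.111 |
| 20-foot lines | 15-16% | 13% | 0.120 |
| Decimal lines | 14-15% | 11% | 0.119-0.121 |
| Letters, 0.02 each | 6.3% | 6.3% | 0.085 |

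In 0.02 steps 0.125 cannot be scored, so the letter figure requires a gain of 0.14 (seven letters). At 0.12 (six letters) it is 9.8%. Part of the gap is therefore a stricter cut, not finer resolution. As a check, the SD of the difference of two readings is √2 × 0.06 = 0.085, so letter scoring adds almost nothing to the reading error itself.

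**Step 3: true gain of 0.2, error SD 0.06.** Metric lines detect about 88% rounded, but only about 69-70% unrounded. Letters detect about 80% at 0.14 and 85% at 0.12. Detection minus false improvement is 88 − 19 = 69 points for rounded metric lines, 80 − 6 = 74 for letters at 0.14, and 85 − 10 = 75 for letters at 0.12.

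**Step 4: effect on mean changes.** The reading-error variance ratio is (0.111/0.085)² = 1.7 to (0.121/0.085)² = 2.0. True change also varies between patients. Take 0.115 as a mid-range value for whole lines, and an assumed SD of true change of 0.15 or 0.25:

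- 0.15: √(0.15² + 0.115²) = 0.189 against √(0.15² + 0.085²) = 0.172, about 10% larger.
- 0.25: √(0.25² + 0.115²) = 0.275 against √(0.25² + 0.085²) = 0.264, about 4% larger.

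Squaring the unrounded ratios (1.096² = 1.20 and 1.042² = 1.09), 50 patients measured by whole lines give a mean change about as precise as 50/1.20 = 42 to 50/1.09 = 46 measured by letters.

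**Step 5: larger reading error.** At error SD 0.10, rounded metric lines give about 27% false improvement against 18% for letters (about 20% against 18% unrounded). Separation of true from false improvement is about 51 points for both rounded metric lines and letters at 0.14. The SD of change is still smaller with letters, 0.141 against 0.157.

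**The case against.** The strongest reply is that the documents do not say the chart is read by whole lines. That is right: a Snellen chart can be scored by letter, and the figures above for Snellen lines apply only if it is not. But no letter-scoring rule is stated either, so nothing in the plan rules out whole-line reading.

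A reader might go further and infer that the smallest change the chart can record always counts as clinically significant. The arithmetic does not support that. Decimal and 20-foot charts have steps well below 0.125, and on the metric chart two of six steps fall just short unless rounded.

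A reader might also infer that the SAP compares responder rates between the arms and that these rates are inflated. The SAP calls 0.125 clinically significant but specifies no count of improved patients and no comparison of such counts; its stated test is an ANOVA on acuity. Only the variance argument applies there, and its size is modest once true variation between patients is included.

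It is also fair that letter scoring looks better partly because its cut rises to 0.14, and that its responder advantage over the rounded metric chart fades when reading error is large. Both are allowed for in the working.

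**Conclusion.** The concern holds in limited form. The plan pairs a Snellen chart with a LogMAR threshold and leaves scoring, conversion and rounding open. If whole lines are read, the threshold is about one metric line. At error SD 0.06, some 11-20% of unchanged patients would appear to improve, depending on layout and rounding, against 6% (or 10% at a 0.12 cut) with letters. The total SD of change would be roughly 4-10% larger.

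Layouts, error SDs, the acuity distribution and the SD of true change are all assumptions; the documents supply none of them. The responder figures matter only if the threshold is used per patient.

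A reader might take this as a bias in favour of one treatment. The documents do not support that: equal error in both arms raises both improvement rates and dilutes their difference. It would favour an arm only if measurement error differed between arms, and the plan gives no evidence that it does. This is a worthwhile, inexpensive improvement rather than a flaw that invalidates the trial.

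**What to change.** **Protocol, item C.** Replace the Snellen chart with an equal-step LogMAR chart scored letter by letter at 0.02 per letter, in a symbol or matching version for children who cannot read letters. Use the same chart and testing distance for each patient at baseline and every follow-up visit.

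**SAP.** Analyse that score directly. Restate the threshold as a whole number of letters, 0.12 (six) or 0.14 (seven), and say whether it applies to each patient or to a mean change. Do not pool preferential-looking results with the LogMAR scores; report them separately.

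**Patients already enrolled.** Keep each on the original chart throughout, and examine their influence in a sensitivity analysis.

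**Cost.** A printed chart and slightly longer testing at visits already planned, with no extra patients, visits or staff. With a 0.14 cut, somewhat fewer true improvers cross the threshold: about 80% against 88% for a true gain of 0.2 at error SD 0.06, compared with rounded metric lines. A 0.12 cut recovers part of that loss (about 85%), at the price of more false improvement (about 10% instead of 6%).

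### Randomised patients who do not complete follow-up are excluded, and the SAP contains nothing to offset the bias this can put into the comparison of the arms

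*Protocol*

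**What the plan says.** The protocol's aim is comparative: "The aim of this work is to compare the gold standard occlusion therapy alone with dichoptic therapy". Under Patients of the study, "Patients will be assigned randomly into two groups", with 50 in each. Under Treatment assessment, acuity is to be followed "after 1 month, after 2 months and after 6 months with regards to visual acuity", and then: "Patients who fail to complete the full time of the follow up period will be excluded from the study".

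The SAP plans summary statistics with confidence intervals. "A one-way analysis of variance (ANOVA) will be performed on the visual acuity data" to look for an effect of measurement time, followed by pairwise comparisons "examining the changes from baseline to 1 month, 3 months and 6 months after treatment start". It adds a threshold of 0.125 logMAR for clinically significant improvement, a proportion-of-change formula, and a compliance percentage per group as a secondary outcome. It does not name an analysis set, a method for missing acuities, a sensitivity analysis, or a report of dropout by arm. It states no between-arm test either; the comparison of arms comes from the protocol's aim.

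The Exclusion Criteria also list "Adult patients and children's parents unwilling to enter or complete the study". As an eligibility criterion this can act only before assignment, so it does not deal with patients who leave later.

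**The concern.** Randomisation makes the two groups of 50 comparable. Removing patients for an event after randomisation means that the groups compared need no longer be the groups randomised. The natural reading of the rule is exclusion from the analysis. The documents do not say that recorded acuities are destroyed or that dropout goes unreported, but 1-month and interim acuities already collected would go unused.

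If poor responders leave one arm more often, or account for dropout in one arm only, that arm looks better than it is. If good responders leave, the sign reverses. The arm difference is unbiased if dropout is unrelated to outcome, or if rate and link are the same in both arms; unequal rates and links could also cancel by chance. The plan contains no analysis that would show which case applies.

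The protocol's introduction makes different dropout plausible. Of patching it says: "Disadvantages include prolonged treatment leading to poor compliance, patching related distress, relationship strain and stigma". It describes the video game as developed to help compliance. This does not establish different dropout, because the rule concerns completing follow-up, not hours of treatment taken.

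Two further quantities are exposed. The within-arm changes from baseline, which are what the SAP actually tests, are distorted by outcome-related dropout even when both arms behave alike. The compliance percentage is overstated if patients who leave complied less.

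**Working it through.** The plan gives no dropout rate, SD, alpha or power, so there is no stated figure to reproduce. The check has two parts: an exact identity, then an illustration on assumed inputs.

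**Identity.** Let q be the share of an arm that drops out and g the mean improvement of completers minus that of dropouts. Then completer mean minus all-randomised mean = q × g. The bias in the difference B − A is qB·gB − qA·gA. It is zero if g = 0 in both arms, or if q and g match. Worked example with assumed values: 30% dropout in A, 10% in B and g = 0.20 in both gives 0.10 × 0.20 − 0.30 × 0.20 = −0.04 logMAR. With 20% in both, gA = 0.20 and gB = 0, it is −0.20 × 0.20 = −0.04. Equal rates did not remove it.

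**Inputs for the illustration.**
- From the documents: 50 randomised per arm; the 0.125 logMAR threshold.
- Assumed: SD of 6-month change 0.15-0.20 logMAR; equal true effects; dropout 10-30%; r, the correlation of dropout propensity with poor change, up to 0.5; a two-sided 5% t-test of completers, since the SAP states none.

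**Formula.** Bias in one arm = r × SD × φ(z_q)/(1 − q), where φ is the standard normal density and z_q its q-quantile. The factor φ(z_q)/(1 − q) is 0.195 at q = 10%, 0.350 at 20% and 0.497 at 30%.

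**(a) Different rates, same link (20-30% v 10%).** Bias = r × SD × difference of factors. Smallest case at r = 0.5: 0.5 × 0.15 × (0.350 − 0.195) = 0.012. Largest: 0.5 × 0.20 × (0.497 − 0.195) = 0.030.

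| r | Bias (logMAR) | Share of 0.125 | False-positive risk |
|---|---|---|---|
| 0 | 0 | 0% | 5% |
| 0.2 | 0.005-0.012 | 4-10% | 5.2-5.8% |
| 0.5 | 0.012-0.030 | 9-24% | 6.4-10.1% |

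A negative r reverses the sign.

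**(b) Equal rates, link in one arm only (r = 0.5 v 0).** Bias = 0.5 × SD × factor.

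| Dropout, both arms | Bias (logMAR) | Share of 0.125 | False-positive risk |
|---|---|---|---|
| 10% | 0.015-0.019 | 12-16% | 7.4% |
| 20% | 0.026-0.035 | 21-28% | 12.1% |
| 30% | 0.037-0.050 | 30-40% | 17.6% |

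With r = 0.2 v 0 at 20% the bias is 0.010-0.014. The false-positive risks use the noncentral t distribution with the completers left from 50 per arm (35-45). They ignore the small reduction in variance from selection, which raises the upper figure in (a) at r = 0.5 to 10.7% and the 20% figure in (b) to 12.5%.

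**Within-arm change.** At r = 0.5 and 20% dropout, each arm's improvement is overstated by the same 0.026-0.035 logMAR, even if the arms match.

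**Compliance.** Overstatement = q × (completer minus dropout compliance). Assuming q = 20% and 80% v 40%: 0.20 × 40 = 8 percentage points; 0 if both comply equally.

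**Range for a sensitivity analysis.** For patients with no post-baseline acuity, the shift that undoes the bias is g = r × SD × φ(z_q)/[q(1 − q)]. At r = 0.5 and q = 10-30% this is 0.124 (0.5 × 0.15 × 0.497/0.30) to 0.195 (0.5 × 0.20 × 0.195/0.10). A range of ±0.125 is too short for most of these cases; ±0.20 covers them.

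**The case against.** The strongest reply is that no harm specific to this trial is shown. The documents give no dropout rate, SD or link to outcome. On the assumptions above the false difference stays at or below 0.050 logMAR, always under the 0.125 threshold, and may be zero. The SAP also states no between-arm test for the rule to distort. This stands as a limit on what can be said about size. It does not rescue the rule: comparison of the arms is the stated aim, any version of it would use completers only, and acuities not collected after a patient is excluded cannot be recovered. A 5% test could be carried to 10-18% in the harder cases without anything in the plan to reveal it.

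A second objection is that a missing-at-random model is not a full cure, and how much it cures depends on the dropout mechanism. That is right. Take |r| of 0.2-0.5, an assumed correlation of 0.5-0.7 between interim and 6-month change, an interim acuity for every dropout and no return at 6 months. The model then leaves about 52-78% of the bias if dropout is driven by the unseen 6-month change, but about 0% if it is driven by the observed interim acuity. If no dropout has an interim acuity and none returns, all of the bias remains. Hence the need for continued follow-up and a sensitivity analysis. The ±0.20 range in turn covers only |r| up to 0.5 and SD up to 0.20.

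Third, the particular model and shift grid are a preference. That is also true: another all-randomised method with a stated missing-data assumption would answer the point.

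**Conclusion.** The concern holds and should be fixed before the analysis. The protocol contains an operative rule that removes randomised patients for a post-randomisation event, and the SAP has nothing to offset it. This is a wrong instruction, not missing detail.

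The conclusion about the rule rests on the text and the identity alone. The size rests wholly on assumptions: with r from 0 to 0.5 and SD of 0.15-0.20 logMAR, the false arm difference is 0-0.030 logMAR for 20-30% v 10% dropout, and up to 0.050 for equal dropout of 30% with a link in one arm only. The documents settle neither its direction nor whether it is zero.

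**What to change.** **Protocol, Treatment assessment.** Replace the exclusion sentence with: 'All randomised patients are analysed in the group assigned; patients who stop treatment or miss a visit are still invited to all remaining scheduled acuity visits, including 6 months.' State that the exclusion criterion on unwillingness applies before randomisation.

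**SAP.** The middle visit is at 2 months in the protocol and 3 months in the SAP. The two must be reconciled before a visit-based model can be written. Then add:

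1. A comparison of arms at 6 months using all available acuities of all randomised patients. One option is a repeated-measures mixed model with baseline as one of the repeated outcomes and terms for visit and for arm by post-baseline visit, so that patients with no post-baseline acuity are included.
2. A missing-not-at-random sensitivity analysis that shifts missing 6-month improvements separately by arm and in both directions, for example −0.20 to +0.20 logMAR including −0.125 and +0.125, and that covers patients with no post-baseline acuity. At 30% v 10% dropout this moves the arm difference by up to 0.30 × 0.20 + 0.10 × 0.20 = 0.08 either way; one common shift moves it by (0.30 − 0.10) × 0.20 = 0.04.
3. Number of dropouts and reasons, by arm.
4. Compliance computed on all randomised patients, with the number missing by arm.
5. Completers only as a secondary analysis.

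**Cost.** One protocol sentence and one SAP paragraph. The visits are already scheduled, but patients must be traced: at 20-30% dropout, 10-15 of the 50 in an arm. The team should confirm that the software named in the SAP can run the chosen analyses. The estimate may be less favourable, and some 6-month values will stay missing. A patient with no post-baseline acuity adds almost no information on change to the main model, so the sensitivity analysis has to carry that case.
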